Aim 2. To assess the feasibility and acceptability of the optimized *MeSSSSage* intervention. In Phase 2 we will evaluate the feasibility and acceptability of two intervention components using a controlled 4-arm factorial design (n=160; 40 per arm): 1) real-time mobile voice information and support group alone, 2) asynchronous/on-demand text-based group support only, and 3) real-time mobile voice information and support group plus asynchronous/on-demand text-based group support. Feasibility and acceptability will be assessed via back-end data, surveys, and IDIs with purposively selected participants (n=30) and moderators.

Aim 3. To explore the preliminary effectiveness of the optimized *MeSSSSage* intervention components on six-month maternal and neonatal health outcomes. Phase 2 data will help us develop a preliminary understanding of the impacts of the intervention components on MCH health-related knowledge, behaviors and outcomes including exclusive breastfeeding, immunization, family planning uptake, postnatal visits, mental health and empowerment; however, it is not statistically powered to formally assess effectiveness.

This study is significant and innovative in addressing key priorities of NICHD's Pregnancy and Perinatology Branch and using systematic, user-centered and experience-driven design approach. These results will inform the most acceptable, feasible, and potentially efficacious intervention design to be robustly tested through an R01 mechanism to assess effectiveness for maternal and infant health outcomes, explore other research questions relevant to intervention development and scale-up for postnatal health among South Asian women, and explore generalizability across populations.

Significance

[figure not shown]

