Sociodemographic characteristics	Age, age at marriage, educational attainment, caste, language spoken, household assets, women's status/decision-making, social support and relationship quality.
Health-related knowledge (effectiveness)	Knowledge on maternal and neonatal danger signs, best practices for infant care, family planning.
Health-related behaviors (effectiveness)	Breastfeeding and complementary food introduction practices (breastfeeding initiation, length of exclusive breastfeeding, length of breastfeeding, timing of complementary food introduction), appropriate management of early childhood illnesses.
Health outcomes (effectiveness)	Early childhood immunization, postnatal depression and anxiety, postnatal family planning adoption.
Intervention perspectives (feasibility, acceptability)	Self-reported engagement in intervention components and topics, satisfaction with intervention components, likelihood of participating again, likelihood of recommending program, value on knowledge and social support gained from participation.

Analysis. *Aim 2. Feasibility and acceptability of the optimized MeSSSSage intervention components.* We will use a mixed methods approach, triangulating data from quantitative baseline and endline data, qualitative IDIs, and technology assessment. Feasibility and acceptability will be measured by participation rates at each session, participation trajectories over time, and user engagement (via technology assessment backend data). Women's reports of use and satisfaction (survey and IDI will shed light on barriers and facilitators to participation. Moderator acceptability will be assessed by satisfaction, fidelity to topic/content based on protocol and perspectives on impact. We will test for differences in feasibility and acceptability between the three intervention arms to understand if both components (group meetings and text) or only one is the best approach, using ANOVA for continuous outcomes and chi-square or Fisher's exact tests, as appropriate, for categorical outcomes.

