Aim 3. Preliminary effectiveness of the MeSSSSage intervention components on six-month MCH outcomes. Using the quantitative survey data, we will statistically evaluate differences by study arm in improvements in women's knowledge, behaviors, and maternal and child health outcomes, compared to the control group (including effect sizes, controlling for relevant socio-demographics as necessary). Figure 1 displays the outcomes that are theoretically related to our intervention targets. Our main *knowledge* outcome will be a composite score representing the proportion of correct answers from a knowledge scale on breastfeeding, newborn and infant care, maternal and infant danger signs, newborn care, and family planning, topics that will be covered within our interactive educational group component. Our main *behavior* outcome will be self-reported exclusive breastfeeding at 6 months. Our main *health related* outcomes will be: (1) completion of early childhood immunization schedule; and (2) postnatal family planning uptake. We will measure women's social support and related mental health status (depression and anxiety) using scales that have been previously validated in similar populations such as the Hopkins Symptom Checklist⁴¹ and the Multidimensional Scale of Perceived Social Support⁴². Finally, women's empowerment will be measured using decision-making and mobility scales.^{43,44}

Sample Size. This pilot development study is not formally powered to detect significant differences in outcomes, but will give insight into directionality of changes. The per group sample size was selected based on feasibility

of recruitment, intervention delivery, and the interpersonal interaction important for a group-focused intervention. The sample is sufficiently large to assess the feasibility and acceptability outcomes through descriptive statistics.

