Where y_i is the outcome for the i^{th} participant, β_0 is the coefficient for the intercept (standard of care), β_1 represents the mean difference in factor 1 (voice), β_2 represents the mean difference in factor 2, (text) β_3 represents the interaction between factor 1 and factor 2 (voice + text), Z_{1i} is the indicator variable for factor 1, Z_{2i} is the indicator variable for factor 2, and ε_i is the residual for the i^{th} participant. Due to the modest sample size, significance testing will be deemphasized and we have not included power analyses for this study.

Hypotheses for preliminary/exploratory analyses on effectiveness. Exploratory hypotheses will be evaluated as part of the study feasibility assessment process. Means and proportions will be plotted by group over time to enable descriptive evaluation of overall patterns of change across time in the outcomes for the intervention and control groups. For example, we expect that following intervention exposure, relative to control group participants, intervention participants will have improved health-related knowledge, health-related behavior, and health outcomes. We also anticipate that intervention participants receiving both voice and text components will have the highest report of the prior outcomes and reported social support, and we will explore differences in these outcomes and in levels of reported social support between the groups as described above.

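### Aim 2 compares voice, text and both through omnibus three-arm tests with no pairwise estimates or intervals, which fits poorly with a sample justified for description and cannot show which arms differ

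*Protocol*

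**What the plan says.** The protocol's Analysis section for Aim 2 states: "We will test for differences in feasibility and acceptability between the three intervention arms to understand if both components (group meetings and text", and the sentence ends "or only one is the best approach, using ANOVA for continuous outcomes and chi-square or Fisher's exact tests, as appropriate, for categorical outcomes". The comparison covers voice alone, text alone and both together; the control arm is not part of it.

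The outcomes are described in the same paragraph: "Feasibility and acceptability will be measured by participation rates at each session, participation trajectories over time, and user engagement". That paragraph also places the tests within a mixed-methods assessment that combines surveys, interviews and back-end data.

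The Phase 2 design is a "controlled 4-arm factorial design (n=160; 40 per arm"). On what that number can support, the protocol's Sample Size section says "This pilot development study is not formally powered to detect significant differences in outcomes" and then "The sample is sufficiently large to assess the feasibility and acceptability outcomes through descriptive statistics".

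The SAP's Quantitative analyses paragraph, which sets out the factorial regression, closes with "Due to the modest sample size, significance testing will be deemphasized and we have not included power analyses for this study". The SAP does not mention the Aim 2 ANOVA or chi-square tests. Neither document plans a pairwise arm contrast, or an interval for one, for feasibility or acceptability.

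**The concern.** The question asked is comparative and directional: is the combination best, or is one component as good? A 2-df omnibus test answers a different question, namely whether the three arms are all the same. If it is significant, it does not say which arms differ. If it is not, the data may still be compatible with a sizeable advantage for one arm. Neither result addresses whether one component suffices.

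The protocol also sizes the sample for description and then names tests, rather than estimates with their uncertainty, as the means of comparing the arms. The pilot's stated purpose is to inform the design of a larger trial. A bare p-value from 40 women per arm gives that decision little to work with, and if grouping is ignored the p-value may not have its nominal error rate either.

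**Working it through.** **Inputs from the documents.** 160 women in 4 arms: 160/4 = 40 per arm, so 3 × 40 = 120 in the Aim 2 comparison. The Phase 2 Procedures and the Recruitment section give two groups per arm and eight in all, so 160/8 = 20 women per group. The Phase 2 overview mentions three groups per modality, but its own total of eight fits only two per arm across four arms. No power calculation exists, so there is no planned power figure to reproduce.

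**Assumed inputs.** Alpha 0.05; a 15-point gap; the arm rates and SDs shown; ICC 0 to 0.10; no dropout unless stated. None of these is in the documents.

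**1. Binary measure, independent women.** The noncentrality of the 3×2 chi-square is λ = n Σ(pᵢ − p̄)² / [p̄(1 − p̄)], with 2 df.
- 70/70/85%: p̄ = 0.75; Σ = 0.05² + 0.05² + 0.10² = 0.015; λ = 40 × 0.015/0.1875 = 3.2; power 34% (simulation 34%).
- 80/80/95%: p̄ = 0.85; λ = 0.6/0.1275 = 4.7; power 48% by the approximation and 51% by simulation.

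Taking one arm higher, one arm lower and evenly spread patterns together, power by the approximation is:

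| Lowest rate | Power for a 15-point gap |
|---|---|
| 50% | 21–27% |
| 60% | 23–31% |
| 70% | 28–39% |
| 75% | 33–48% |
| 80% | 43–63% |

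With 20% dropout (32 per arm) and a lowest rate of 70%, power is 23–32%.

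**2. Continuous participation score, independent women.** Noncentral F on 2 and 117 df, with λ = n Σ(μᵢ − μ̄)²/SD². Example: one arm 15 points higher, SD 20. The standardised gap is 0.75, Σ = 0.25² + 0.25² + 0.50² = 0.375, λ = 15, power 94%. Over the one-arm-higher and evenly spread patterns:

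| SD (points) | ANOVA power for a 15-point gap |
|---|---|
| 20 | 85–94% |
| 25 | 66–79% |
| 30 | 49–62% |
| 35 | 38–48% |
| 40 | 30–38% |

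**3. Grouping.** Beta-binomial simulation, two groups of 20 per arm, chi-square applied as if women were independent:

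| ICC | Rejection with all arms at 70% (nominal 5%) | Rejection at 70/70/85% |
|---|---|---|
| 0 | 5% | 34% |
| 0.02 | about 12% | 41% |
| 0.05 | 22% | 48% |
| 0.10 | 37% | 56% |

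The higher rejection rates in the last column are not real power, because the false-positive rate has risen too.

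**4. What pairwise intervals would show.** At 80% in both arms the 95% half-width is 1.96 × √(2 × 0.8 × 0.2/40) = 0.175, or ±17.5 points. For 70% against 85% it is 1.96 × √(0.21/40 + 0.1275/40) = 0.180. Multiplying the first by √(1 + 19 × ICC) gives about ±20.6, ±24.5 and ±29.9 points at ICC 0.02, 0.05 and 0.10. With only two groups per arm the ICC is itself poorly estimated, so these normal-quantile widths are still optimistic.

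**The case against.** The strongest reply is that this is openly an unpowered pilot and that no p-value is said to choose the arm. The tests are there to aid understanding, beside ten interviews per intervention condition, moderator questionnaires and interviews, and back-end data. Arm-level descriptive results would show the direction behind a significant test. All of that stands, and it rules out several stronger readings that a reader might infer:

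- *The test decides the design.* The documents do not say so, nor do they say that non-significance will be taken as equivalence. The risk is that the plan leaves room for that reading.
- *The protocol contradicts the SAP.* De-emphasising tests is not omitting them, and the SAP's sentence belongs to the factorial regression. It is a mismatch of emphasis. The clearer tension is inside the protocol, between the Sample Size section and the Aim 2 analysis.
- *The test usually misses a 15-point difference.* This holds for binary measures with a lowest rate of about 50–75% and independent women. It does not hold generally near the ceiling, or for participation scores with an SD below about 30 points. The 15-point gap is itself an assumption.
- *No difference is the likeliest finding.* Not necessarily: with an ICC of 0.05 the naive test rejects in 48% of trials at 70/70/85%, partly because it is miscalibrated.

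A rule on one acceptability measure, carrying forward the top-ranked arm unless the leaders fall within a margin and then taking the simpler one, is also tempting. At 70/70/85% pure ranking puts the best arm first about 91% of the time (independent women, ties broken at random). That figure does not describe the rule with a margin: if the combined arm is truly best, it goes forward in only about 72%, 49% and 26% of trials at margins of 5, 10 and 15 points. A single measure would also set aside feasibility, moderator effort and the interviews.

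The reply does not supply the missing element: a planned estimate of each arm difference with its uncertainty.

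**Conclusion.** The point holds as a mismatch between question, method and sample. That part needs no assumed effect size: an omnibus test cannot say which arms differ or that one component is enough, and no pairwise estimate or interval is planned.

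The size of the problem depends on assumptions. At alpha 0.05 with independent women, power for a 15-point binary gap is about 34% at 70/70/85% and about 51% at 80/80/95%. For a continuous participation score it runs from about 30% (SD 40) to 94% (SD 20). If the two groups per arm are ignored, the false-positive rate at a 70% rate is about 12–37% for an ICC of 0.02–0.10. The omnibus p-value may therefore mislead in either direction.

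The documents do not support a claim that the pilot will select the wrong arm, or that its design choice rests on this test alone.

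**What to change.** In the protocol's Aim 2 analysis, and in the SAP, which is silent on it:

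1. For each feasibility and acceptability measure compared between arms, make the three pairwise differences (voice against text, voice against both, text against both) with 95% CIs the main comparison.
2. Compute the intervals with allowance for the two groups per arm, or report them unadjusted with a stated range of ICCs and a warning that they are too narrow.
3. Drop the omnibus p-value or label it secondary.
4. State that a non-significant result will not be read as equivalence or as evidence that one component suffices.
5. Leave the choice of design within the triangulated assessment; do not add a single-measure selection rule with a margin favouring the simpler arm.

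This changes wording and output tables only; it needs no extra women or data. The downside is that the intervals will be wide, and will show openly that the pilot cannot firmly separate the arms.

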In-depth interviews: Additionally, in-depth interviews (IDIs) will be conducted with a selection of 10 women from each intervention condition (30 IDIs), purposively sampled based on high/low participation rates determined by the end line survey. We will collect data on experiences with *MeSSSSage* and how to improve it.

Technology assessment: Finally, we will collect and analyze the quantitative backend data from the prototype to gain more insight into women's participation in the intervention, including attendance and level of participation

in group interactive educational sessions, use of mobile social support platform (number of posts, frequency, topic), etc. Text data from transcripts of the educational sessions and content of group messaging will be analyzed for content in order to understand primary educational needs and interests for postnatal women.

Group moderator survey and interview: ASHA facilitators moderating the groups will be asked to respond to a short questionnaire after each group session to understand: preparation and delivery time, content, efficiency, acceptability and satisfaction with the group model, perspectives of impact, challenges, and any follow-up/referral necessary.⁴⁰ Regarding facilitation of groups that receive the text-based messaging intervention component only, ASHA facilitators will report on experiences in the prior week. We will conduct monthly semi-structured interviews with each of the ASHA facilitators to understand their preferences for group components, experiences preparing for and conducting the sessions, and their perspectives on mobile provision of education, care, and support.

Measures: The baseline survey content will include sociodemographic characteristics and knowledge about maternal and infant health, self-efficacy, and perceived social norms regarding MCH-related health promoting behaviors. The endline survey will include acceptability questions such as women's satisfaction with and perceptions of *MeSSSSage*, maternal and infant knowledge-, behavior-, and health-related questions including about breastfeeding, complementary food introduction, immunization, family planning uptake, maternal physical and mental health, etc. which have previously been used in this setting (Table 3)⁴.

Table 3: Participant survey measures (Phase 2)

Category	Measures

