Phase 2: 18+ years old, primiparous (pregnant with their first birth)

Prospective participants will be screened for eligibility by the local community health worker (ASHA) and a member of the research staff. Research assistants will read through the consent form with prospective participants and will assess that they understand what the study involves, including risks and benefits, and that the participant is sufficiently oriented to make an informed decision regarding study participation. Study participants will be asked for multiple forms of contact information.

All recruitment and consent procedures are detailed more fully below. All research procedures described in this application will be overseen by UCSF's and the Postgraduate Institute of Medical Education and Research (PGIMER) Human Subjects Protection Committees/IRB.

Potential Risks to Participants (Phase 2)

The overall risk to participate in this study is minimal.

Psychological Distress. The group will focus on issues important to maternal and child health care during the postpartum period, so it is unanticipated but possible that participants may experience psychological distress if discussing issues around maternal and infant health, postpartum mental health or social support.

Confidentiality: There is the potential for violation of participant confidentiality, but we believe the safeguards that we have integrated into the study methodology, as described below, will effectively limit this risk.

Adequacy of Protection Against Risks

Participants will be recruited by the local community health worker (ASHA) and a member of the research assistant, who will be trained and supervised by study staff. Recruitment will occur in the last month of pregnancy in the woman's home. Study staff will answer any questions potential participants may have. During the consent process for study participation, study staff members will describe the details of the nature of the participant's involvement in the study, the possible risks and benefits of participation, and the ability to withdraw from the study at any time without consequence. The participant will have the opportunity to ask questions about the study, after which written consent will be obtained.

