Text-based, asynchronous, on-demand social support: App-based small group text-based communication. Moderated by health professional. (text)		X	X	
Standard of care: 3 visits in the first 7 days postnatal (facility and home)	X	X	X	X

The following intervention characteristics will be assessed:

Feasibility. To evaluate feasibility of the intervention, we will monitor enrollment rates and moderator effort required (e.g. number of staff hours). An enrollment rate of 70% or higher will be considered feasible, as the established standard in intervention literature. Through moderator report we will confirm effort required for preparation, session delivery, and follow-up. We will also capture any technological challenges. This information will inform staffing needs and retention protocols for a subsequent full trial.

Acceptability. To measure acceptability, we will use a client satisfaction questionnaire which will capture self-reported engagement in intervention components and topics, satisfaction with intervention components, likelihood of participating again, likelihood of recommending program, and value on knowledge and social support gained from participation.

Preliminary effectiveness. To measure effectiveness, we will health-related knowledge (maternal and neonatal danger signs, best practices for infant care, and family planning), health-related behaviors (breastfeeding and complementary food introduction practices (breastfeeding initiation, length of exclusive breastfeeding, length of breastfeeding, timing of complementary food introduction), appropriate management of early childhood

illnesses), and health outcomes (Early childhood immunization, postnatal depression and anxiety, postnatal contraceptive adoption.)

Quantitative analyses: With a between-groups design, each participant will participate in only one arm of the trial, thus we will assess quantitative intervention outcomes by factor (voice and text) through fitting a series of the following linear regression model:

$$y_i = \beta_0 + \beta_1 Z_{1i} + \beta_2 Z_{2i} + \beta_3 Z_{1i}Z_{2i} + \varepsilon_i$$

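### The protocol's Aim 3 section allows conditional, unnamed covariate adjustment, while the printed model in both documents has none; one fixed model per outcome should be named.

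*Protocol*

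**What the plan says.** Three places describe the Aim 3 comparison.

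- Protocol, Analysis, Aim 3: the survey data will be used to evaluate "differences by study arm in improvements in women's knowledge, behaviors" and health outcomes against control, with effect sizes, "controlling for relevant socio-demographics as necessary". No covariate is named, no condition for adjusting is given, and no estimate is designated as the main one.
- Protocol, Statistical Design and Power, Quantitative analyses: outcomes are assessed by factor with a linear model containing an intercept, voice, text and voice x text. There is no covariate and no baseline term.
- SAP, Quantitative analyses: the same model, again "through fitting a series of the following linear regression model".

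The candidates for adjustment are in protocol Table 3, under sociodemographic characteristics: "Age, age at marriage, educational attainment, caste, language spoken, household assets, women's status/decision-making, social support and relationship quality". That is nine items, or eight if the last two are taken as one. The Measures paragraph says the baseline survey covers "sociodemographic characteristics and knowledge about maternal and infant health, self-efficacy, and perceived social norms".

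Aim 3 has four main outcomes: a knowledge score, "self-reported exclusive breastfeeding at 6 months", completion of the immunization schedule, and postnatal family planning uptake. Women are recruited in their first pregnancy, so only the knowledge score has a baseline value of its own.

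**The concern.** The voice coefficient in the printed model is the voice-only versus control difference, which is also one of the contrasts in the Aim 3 section. The same quantity therefore has two prescribed estimators. One of them is open-ended, because whether to adjust, and for what, can be settled after the arm-level data are seen. The conflict lies inside the protocol as well as between protocol and SAP, so amending the SAP alone would not remove it.

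Aim 3 promises effect sizes, and the protocol says the pilot will inform the design of a larger trial. If the reported estimate is the most favourable of several, the effect carried forward is too large and its interval too narrow, whether or not a p-value is quoted.

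**Working it through.** **Inputs from the documents.** There are 160 women in 4 arms of 40 (4 x 40 = 160, which agrees with the stated total). Allocation is by random number generator with no stratification factor named. No alpha, SD, effect size or power calculation is given, so there is no power figure to reproduce. **Assumptions.** Two-sided 5% level; independent covariates of equal strength; the share of variance they explain (R2) is varied. Clustering by support group is ignored and would widen every interval.

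**1. Yardstick.** The SE of an arm-versus-control contrast is SD x sqrt(2/40) = 0.2236 SD. With 160 - 4 = 156 residual degrees of freedom, the 95% half-width is 0.442 SD.

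**2. How many estimates are admissible.** Nine candidates give up to 2^9 = 512 adjustment sets per outcome and contrast. A more modest menu of ten models is the unadjusted model, eight one-covariate models, and one model with all eight.

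**3. Error rate with no true effect** (voice-only versus control, eight covariates, joint R2 = 0.20; repeated runs of 4,000 to 6,000 simulated trials where the number is recorded, simulation error 0.3 to 0.5 points):

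| Rule | Rejection rate |
|---|---|
| Always unadjusted | 4.7-5.5% |
| Always adjusted for all eight | 5.1-5.3% |
| Adjust only for covariates that differ at baseline (p < 0.05) | 4.6-4.9% |
| Report the most favourable of the ten models | 9.5-10.3% |

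At R2 = 0.10 the last figure is 8.0%. At R2 = 0.40 the imbalance-triggered rule gives 4.1-4.3%. With nine covariates (1,500 trials per R2, error about 1 point), taking the better of unadjusted and fully adjusted gives about 6-8%. Taking the best of all 512 sets gives 9% at R2 = 0, 12% at 0.10, 15% at 0.25 and 23% at 0.40.

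**4. Movement in the estimate itself.** The median gap between the smallest and largest of the ten estimates is 0.10-0.14 SD. That is 0.10/0.442 = 23% to 0.14/0.442 = 32% of the half-width. Over all 512 sets it is 0.10, 0.18, 0.26 and 0.33 SD at the four R2 values above.

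**5. What fixed adjustment buys.** For two covariates the variance factor is (1 - R2) x (1 + 2/153), and the interval width scales with its square root.

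- R2 = 0: sqrt(1.013) = 1.007, about 0.7% wider.
- R2 = 0.05: sqrt(0.962) = 0.981, 1.9% narrower.
- R2 = 0.10 and 0.20: 4.5% and 10.0% narrower. Ignoring the lost degrees of freedom, 1 - sqrt(1 - R2) gives 5.1% and 10.6%.

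If eight equally strong covariates jointly explain 20%, any two explain 2/8 x 20% = 5%, which is the 1.9% case.

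For the knowledge score, adding baseline knowledge with baseline-endline correlation rho gives a factor (1 - rho^2) x (1 + 1/154). The half-width becomes 0.441 SD at rho = 0.1, 0.423 at 0.3, 0.384 at 0.5 and 0.316 at 0.7. The documents give no value for rho.

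**The case against.** The strongest reply is that Aim 3 makes no confirmatory claim. The protocol and SAP call it unpowered and de-emphasize significance testing, so a type I error rate is a poor measure of harm. That is fair, and it limits the severity. It does not settle which effect size is to be reported, and the spread in step 4 matters without any test.

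A second reply is that the ordinary reading of the protocol's clause is adjustment for baseline imbalance, which is harmless to the error rate. Step 3 bears this out. A reader might infer that conditional adjustment by itself makes intervals too narrow, and might point out that eight tests flag at least one imbalance in 1 - 0.95^8 = 34% of trials. The calculations do not support that inference: only selection on the result inflates error. Nor is chance imbalance a defect in the unadjusted analysis. At the 75% state-wide literacy the protocol quotes, the difference between two arms has a 95% range of 1.96 x sqrt(2 x 0.75 x 0.25/40) = +/-19 points, but the unadjusted interval already allows for this.

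A reader might also infer from the protocol's paragraph on low literacy that education is expected to affect engagement and must therefore be prognostic. That paragraph calls an effect possible, then says the team has not met the problem in earlier projects and anticipates that these women will be more literate than average. Engagement with the intervention also arises only in the intervention arms. The documents do not show that education, or any other covariate, predicts the Aim 3 outcomes.

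Finally, it would be too strong to say that a free precision gain is forgone. The Aim 3 section permits adjustment, and for the three outcomes without a baseline value the gain could be nil.

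**Conclusion.** The inconsistency stands. One section of the protocol allows unspecified, conditional adjustment; another section of the protocol and the SAP specify none; no text ranks them. The consequence is an avoidable choice among estimates that typically span 0.10-0.14 SD. If the most favourable of ten were reported, the error rate would roughly double, to about 9-10% at an assumed joint R2 of 0.20. That is an upper bound for that set of models, because it assumes the smallest p-value is deliberately chosen. A larger menu would raise it, a weaker R2 would lower it, and nothing in the documents suggests such selection is intended.

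This does not threaten the pilot's validity or its feasibility and acceptability aims. It should be corrected because the Aim 3 effect sizes are meant to inform the larger trial and the remedy is cheap. The case for fixed adjustment rests on having a single pre-stated estimate; precision is a possible bonus of unknown size.

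**What to change.** Before arm-level data are seen, state one main model per Aim 3 outcome: the printed factorial model plus a small fixed set of baseline covariates, kept regardless of observed imbalance. Educational attainment and maternal age would serve as examples, with baseline knowledge added for the knowledge score. The team may prefer other covariates; what matters is that they are named in advance. With baseline knowledge in the model, the arm coefficients are the same whether endline or change is the response, which also settles what improvement means for that score.

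Report the unadjusted model beside the main one for every outcome. Replace the conditional clause in the protocol's Aim 3 analysis with a reference to this model, and amend the Quantitative analyses text in both the protocol's Statistical Design and Power section and the SAP so that all three agree.

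The cost is wording in three places and two or three of 156 residual degrees of freedom, provided each covariate enters as a single term (coding education in several categories would use more). No new data are needed, since all of these items are already in the planned survey. If the covariates prove unrelated to an outcome, its intervals widen by under 1% with two of them.
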